### **7.4 Dosing delays and modifications once at least MLFS is achieved**

Each subsequent cycle of treatment with decitabine+venetoclax should be administered as per the FDA decitabine/venetoclax label. Per the label, if grade 4 thrombocytopenia and/or neutropenia occurs, hold both decitabine and venetoclax until the neutropenia and thrombocytopenia resolve to a grade 2 or less. Please refer to Section 6.5.1 for further details. If a decitabine/venetoclax cycle is delayed, nivolumab should also be held and then restarted on Day 1 of the next cycle when decitabine/venetoclax is restarted.

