### 6.5.1 Duration of Therapy in cases of CR

If the patient achieves a CR/CRi, even if MRD negative, the patient should continue on therapy as long as none of the above instances in 6.5 occurs. However, venetoclax may be interrupted, and the subsequent cycle of decitabine may be delayed to allow for absolute neutrophil count recovery from day 29 of current cycle until absolute neutrophil count reached at least 500/ $\mu$ L or

up to 14 days, then a bone marrow biopsy should be done to assess for continued CR/CRi. If patient remains in CR/CRi then dose reductions can occur as follows. For recurrent Grade 4 neutropenia and thrombocytopenia that lasts >6 weeks from Day 1 of cycle: first dose reduction will be to decrease venetoclax to 14 days (days 1-14 of the cycle), the second dose reduction will be to decreased to 7 days (days 1-7 of the cycle), the third dose reduction will be to reduce decitabine to 4 days (days 1-4 of the cycle), and the fourth/final dose reduction will be to reduce decitabine to 3 days (days 1-3 of the cycle). If Grade 4 thrombocytopenia and neutropenia recurs after all of these four dose reductions and lasting >56 days, patient will be taken off study.

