# **7. DOSING DELAYS/DOSE MODIFICATIONS**

## **7.1 Dose Delays/Modifications for DLT**

Study treatment (all three drugs) will be held for any patients experiencing a DLT.

Non-hematologic DLT: Patients may restart therapy when the adverse event recovers to CTCAE  $\leq$ grade 1 or to the patient's baseline values. If study treatment is restarted and another non-hematologic DLT is encountered, the patient must be removed from the study.

Hematologic DLT: After the 42 day period and confirmed hematologic DLT: If peripheral blasts are absent AND the bone marrow blasts are less than 5%, then the patient may restart study treatment with decrease of decitabine to 5 days from 10 days of therapy.

If treatment is delayed >6 weeks for an adverse event the patient must be permanently discontinued from study therapy.

Patients requiring > two dose delays for the same event should go off protocol therapy.

Please see specific modifications for Nivolumab (Section 7.3)

Drugs may be resumed per protocol. If a specific agent (e.g. decitabine or nivolumab or venetoclax) is permanently discontinued for toxicity, the other two agents may be continued on study. Decitabine and venetoclax doses should not be reduced following toxicity and dose interruption, they should continue at the same dose as stated in the protocol.

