#### Morphologic Leukemia-free State (MLFS)

MLFS requires all of the following:

- 12.1.1 < 5% blasts in bone marrow aspirate
- 12.1.2 No extramedullary disease
- 12.1.3 No blasts with Auer rods

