### **Morphologic CR with incomplete blood count recovery (CRi)**

CRi requires all of the following:

- 12.1.17** < 5% blasts in bone marrow aspirate
- 12.1.18** Neutrophils < 1,000/ $\mu$ L or Platelets < 100,000/ $\mu$ L
- 12.1.19** No extramedullary disease
- 12.1.20** No blasts with Auer rods detected
- 12.1.21** If blood counts recover within 14 days of a bone marrow evaluation that is consistent with CRi, the patient will be considered CR at the time when both neutrophil and platelet count recover (neutrophils  $\geq$  1,000/ $\mu$ L, platelets  $\geq$  100,000/ $\mu$ L).

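### At dose level -2 the first cytopenia reduction step leaves venetoclax unchanged; secondarily, 6.5.1 and 7.4 do not say which governs restart in responders

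*Combined protocol and SAP*

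**What the plan says.** **Dose levels.** In the Section 6.1 table the three levels share the same decitabine and nivolumab. Venetoclax is 400 mg daily after the ramp-up, and the levels differ only in the number of venetoclax days. DL 1 gives Days 1-28 in induction and Days 1-21 in maintenance. DL -1 gives Days 1-21 and DL -2 gives Days 1-14, in cycle 1 and in every later cycle.

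**Reduction ladder.** Sections 6.5.1 and 7.2 list the same four steps in the same order: venetoclax to 14 days, venetoclax to 7 days, decitabine to 4 days, decitabine to 3 days. The trigger in 6.5.1 opens "For recurrent Grade 4 neutropenia and thrombocytopenia that lasts" more than six weeks from Day 1 of the cycle. A patient leaves the study if grade 4 counts recur after all four reductions and last more than 56 days. Neither section distinguishes between dose levels.

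**Restart after a hold.** Section 7.4 applies once a patient has reached at least MLFS. For grade 4 neutropenia and/or thrombocytopenia it says to "hold both decitabine and venetoclax until the neutropenia and thrombocytopenia resolve to a grade 2 or less", and then adds: "Please refer to Section 6.5.1 for further details". Section 6.5.1 applies to patients in CR or CRi. It permits venetoclax to be interrupted and the next decitabine cycle to be delayed to allow for "absolute neutrophil count recovery from day 29 of current cycle until absolute neutrophil count reached at least 500" per microlitre, or for "up to 14 days, then a bone marrow biopsy should be done to assess for continued CR/CRi". It names no platelet count.

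**The concern.** A ladder of reductions protects a patient only if each step lowers exposure. At DL -2 the first step names the schedule the patient is already on. DL -2 would be in use only because two higher venetoclax exposures had proved too toxic, so this is the level where an ineffective first step is least welcome.

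The restart rules raise a lesser question of consistency. A responder held for grade 4 thrombocytopenia may reach a neutrophil count of 500 while platelets lag. The wait described in 6.5.1 is then over, but the hold in 7.4 is not. If sites differ on which section controls, patients with the same counts could be managed differently. Because 7.4 also ties nivolumab to the decitabine/venetoclax restart, all three drugs would move together.

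**Working it through.** **1. The first ladder step at each level.** Inputs are the venetoclax days in 6.1, the 400 mg daily dose, and the first step of 14 days in 6.5.1 and 7.2. The plan states no figure of its own to reproduce. Exposure per cycle = days x 400 mg. Cycle 1 is left out because of the ramp-up.

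| Level and phase | Days before | mg before | Days after step 1 | mg after | Change |
|---|---|---|---|---|---|
| DL 1, induction cycles 2-3 | 28 | 11,200 | 14 | 5,600 | -50% |
| DL 1, maintenance | 21 | 8,400 | 14 | 5,600 | -33% |
| DL -1, cycle 2 onward | 21 | 8,400 | 14 | 5,600 | -33% |
| DL -2, cycle 2 onward | 14 | 5,600 | 14 | 5,600 | 0% |

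The first cut that has any effect at DL -2 is the second step: 7 x 400 = 2,800 mg, which is -50% from 5,600. So 4 - 1 = 3 of the four listed reductions change treatment at that level. If the daily dose is lowered for a CYP3A inhibitor (6.4.1.1), the milligrams shrink but the day counts do not, so the DL -2 change is still zero.

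**2. How likely DL -2 is to be used.** The documents give no expected DLT rate, so this is an assumption shown over a range. Under the 3+3 rules in 9.1 a level fails with two or more DLTs in six patients. With independent patients and true DLT rate p, P(fail) = 1 - [(1-p)^6 + 6p(1-p)^5].

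- p = 0.1: 0.114
- p = 0.2: 0.345
- p = 0.3: 0.580
- p = 0.4: 0.767

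Reaching DL -2 needs DL 1 and DL -1 both to fail. With the same p at both levels the product is 0.013, 0.119, 0.336 and 0.588. The chance therefore runs from about 1% to about 59%, depending on a rate nobody yet knows.

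**3. Who falls under both restart rules.** Section 12.1 says "MLFS requires all of the following" and lists marrow blasts below 5%, no extramedullary disease and no Auer rods. For CRi it says "CRi requires all of the following" and lists those same three with a count condition. CR also contains all three. Every patient in CR or CRi has therefore reached at least MLFS, and every patient covered by 6.5.1 is also covered by 7.4.

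**4. The two rules side by side.**

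- Lineages: neutrophils only in 6.5.1; neutrophils and platelets in 7.4.
- Level: a neutrophil count of 500 in 6.5.1; grade 2 or less in 7.4.
- Time limit: 14 days counted from Day 29 in 6.5.1, so to Day 42 (28 + 14); none in 7.4.
- What follows: a marrow, then possible reductions, in 6.5.1; restart in 7.4.
- Precedence: none stated. The pointer from 7.4 to 6.5.1 does not say whether the neutrophil threshold replaces the grade 2 rule or sits inside it.

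The mismatch does not depend on CTCAE cut-offs, because the lineages and time limits already differ.

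**5. Effect on the design.** The rule in 9.1 (13 or more responses in 30; 30% against 50%) recomputes to 0.0845 and 0.1808, in line with the stated 0.084 and 0.181. Nothing above enters that calculation.

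**The case against.** **On the ladder.** A sensible clinician, told to decrease venetoclax in a patient already on 14 days, would go to 7. That is likely in practice, but both sections fix the order of steps and count four of them before removal, so the literal text still uses up one step on no change. It could also be said that the general statements of Days 1-21 for maintenance (Schema, the regimen table in 6.1, the study calendar) apply at DL -2, which would make the first step a real cut. The level-specific row in 6.1 says otherwise, and 21 days would undo the de-escalation. The objection that the problem is doubly conditional stands: the trial must de-escalate twice, and a patient must then have recurrent, prolonged grade 4 cytopenia.

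**On restart.** This objection is strong. Section 6.5.1 is permissive, and what it leads to is a marrow, not an instruction to re-dose. Section 7.4 holds the only explicit condition for ending a hold, and a site that follows it breaches neither section. A reader might infer that 6.5.1 authorises re-dosing with unrecovered platelets. The documents do not say so; 6.5.1 is simply silent on counts at that point. What remains is a missing statement of precedence.

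**Conclusion.** The ladder point holds on the text of 6.1, 6.5.1 and 7.2. At DL -2 the first step is a 0% change where other levels get -33% or more. On a literal reading, a qualifying patient waits for a further episode before exposure falls. The restart point is a secondary ambiguity that one sentence would settle.

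Two stronger readings are not supported. A reader might infer that, if DL -2 became the MTD, all 30 patients treated there would be affected; only those who meet the ladder trigger would be. A reader might also derive a fixed maximum gap between the two restart dates by pairing Day 42 with the rule in 7.1, "If treatment is delayed >6 weeks for an adverse event the patient must be permanently discontinued from study therapy". Section 7.1 is headed for DLT and 7.4 does not invoke it. The neutrophil wait can end well before Day 42. Sections 6.5.1 and 7.2 place removal for grade 4 cytopenia after four reductions and more than 56 days. The documents set no such bound.

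This is a dosing-safety correction. It leaves sample size, dose-level assignment and the stated error rates as they are.

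**What to change.** 1. In 6.5.1 and 7.2, state that at DL -2 the ladder begins at venetoclax Days 1-7. In both sections, make removal depend on exhausting every reduction that applies at the patient's level (three at DL -2, four otherwise). Without this second change the four-step removal condition could not literally be met at DL -2. Cost: one fewer nominal step before removal.

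2. In 7.4, state that its two-lineage criterion governs restart and that the 14-day point in 6.5.1 triggers the marrow only. Cost: longer holds for some responders whose platelets recover late.

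Both are wording changes. Neither alters the visit schedule or the decision rule.

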### **7.5 Nivolumab**

Please refer to the Nivolumab Investigator Brochure or Appendix E to the protocol for toxicity management algorithms which include specific treatment guidelines. These algorithms should

be followed unless there are specific clinical circumstances for which the treating physician decides an alternative treatment approach is clinically appropriate. Consultation with the study PI or drug monitor is recommended.

Adverse events associated with Nivolumab exposure may represent an immunologic etiology. These AEs may occur shortly after the first dose or several months after the last dose of treatment. Nivolumab must be withheld for drug-related toxicities and severe or life-threatening AES.

- **Drug will be held for any indication suggestion of cardiac dysfunction of any grade pending evaluation**
- **Drug will be permanently discontinued for treatment related grade 3 or 4 cardiac dysfunction and grade 2 events that do not recover to baseline or that reoccur**
- **Treatment as clinically indicated for cardiomyopathy**

Cardiac *	Management/Next Dose for Nivolumab Cardiac Toxicities
Less than grade 2	Hold dose pending evaluation and observation.** Evaluate for signs and symptoms of CHF, ischemia, arrhythmia or myositis. Obtain history EKG, CK (for concomitant myositis), CK-MB. Repeat troponin, CK and EKG 2-3 days. If troponin and labs normalize without evidence of myocarditis may resume therapy. If labs worsen or symptoms develop then treat as below.
Grade $\geq 2$ with suspected myocarditis	Hold dose. Admit to hospital. Cardiology consult. Rule out MI and other causes of cardiac disease. Cardiac Monitoring. Cardiac Echo. Consider cardiac MRI and cardiac biopsy. Initiate high dose methylprednisolone and immune suppression as clinically indicated. If no improvement within 24 hours consider adding either infliximab, ATG or tacrolimus.. May resume therapy if there is a return to baseline and myocarditis is excluded or considered unlikely.
Grade $\geq 2$ with confirmed myocarditis	Off protocol therapy. Admit to CCU (consider transfer to nearest Cardiac Transplant Unit). Treat as above. Consider high dose methylprednisolone Add ATG or tacrolimus if no improvement. Off protocol treatment.

*Including CHF, LV systolic dysfunction, Myocarditis, CPK, and troponin
 
**Patients with evidence of myositis without myocarditis may be treated according as “other event”
 
Note: The optimal treatment regimen for immune mediated myocarditis has not been established. Since this toxicity has caused patient deaths, an aggressive approach is recommended.
	

All Other Events	Management/Next Dose for Nivolumab
$\leq$ Grade 1	No change in dose.
Grade 2	Hold until $\leq$ Grade 1 OR baseline (exceptions as noted below).
Grade 3	Hold until $\leq$ Grade 1 OR baseline and patient no longer on steroid treatment if initiated (exceptions as noted below). Permanently discontinue for events with a high likelihood of morbidity or mortality with recurrent events.
Grade 4	Off protocol therapy.
Recommended management: As clinically indicated	

- Any Grade 2 drug-related uveitis or eye pain or blurred vision that does not respond to topical therapy and does not improve to Grade 1 severity within the re-treatment period OR requires systemic treatment should go off protocol treatment
- Any Grade 3 or 4 drug-related laboratory abnormality or electrolyte abnormality, that can be managed independently from underlying organ pathology with electrolyte replacement, hormone replacement, insulin or that does not require treatment **does not** require discontinuation.
- Any AE, laboratory abnormality, or intercurrent illness which, in the judgment of the investigator, presents a substantial clinical risk to the subject with continued study drug dosing should go off protocol treatment.

Skin Rash and Oral Lesions	Management/Next Dose for Nivolumab
≤ Grade 1	No change in dose*.
Grade 2	Hold* until 1≤ Grade resolved. Resume at same dose level.
Grade 3	Hold* until ≤ Grade 1. Resume at same level at investigator discretion
Grade 4	Off protocol therapy.

\*Patients with purpuric or bullous lesions must be evaluated for vasculitis, Steven-Johnson syndrome, toxic epidermal necrolysis (TEN), and autoimmune bullous disease including oral lesions of bullous pemphigus/pemphigoid. Pruritus may occur with or without skin rash and should be treated symptomatically if there is no associated liver or GI toxicity. Note skin rash typically occurs early and may be followed by additional events particularly during steroids tapering.

Recommended management: AE management guidelines

Liver Function AST, ALT, Bilirubin	Management/Next Dose for Nivolumab
≤ Grade 1	Hold at investigator discretion until ULN or baseline. Resume at same dose level.
Grade 2	Grade 2 (3X UNL to 5X UNL): Hold until grade 1 (UNL-3X UNL) or baseline. Resume at same dose level at investigator discretion.
Grade 3	Grade 3 (5X UNL to 20X UNL) Hold until grade 1 or baseline. Resume at same dose level at investigator discretion with return to grade 1 or baseline within 7 days without steroids. If persistent or steroids are required, off protocol therapy.
Grade 4	Off protocol therapy.

Continued treatment of active immune mediated hepatitis may exacerbate ongoing inflammation.

Holding drug to evaluate liver function test (LFT) changes and early treatment are recommended. LFT changes may occur during steroid tapers from other events and may occur together with other GI events including cholecystitis/pancreatitis.

Please note: Grades for liver function follow UNL rather than multiples of baseline.

Recommended management: see Hepatic AE management algorithm

Diarrhea/ Colitis	Management/Next Dose for Nivolumab
≤ Grade 1	Hold until baseline. No change in dose.
Grade 2	Hold until baseline. No change in dose.
Grade 3	Resume at same dose level at investigator discretion if resolved to grade 1 within 7 days without steroids and no evidence of colitis. If persistent or steroids are required off protocol therapy.
Grade 4	Off protocol therapy.
See GI AE Algorithm for management of symptomatic colitis.	
Patients with Grade 2 symptoms but normal colonoscopy and biopsies may be retreated after resolution.	
Patients who require systemic steroids should be taken off study treatment.	
Please evaluate pituitary function prior to starting steroids if possible without compromising acute care. Evaluation for all patients for additional causes includes C. diff , acute and self-limited infectious and foodborne illness, ischemic bowel, diverticulitis, and IBD.	
Recommended management: see GI AE management Algorithm	

Pancreatitis Amylase/Lipase	Management/Next Dose for Nivolumab
≤ Grade 1	Continue at same dose level if asymptomatic at investigator discretion.
Grade 2	Continue at same dose level if asymptomatic at investigator discretion. If symptomatic, resume at same dose level when resolved
Grade 3	Continue at same dose level if asymptomatic at investigator discretion. Patients should have imaging study when clinically indicated (grade 3 symptomatic pancreatitis) before resuming treatment. Patients who develop diabetes mellitus should be taken off treatment.
Grade 4	Hold until grade 2. Resume at same dose level if asymptomatic. Patients who are symptomatic should have imaging study prior to resuming treatment and when clinically indicated. Patients who develop grade 4 symptomatic pancreatitis or diabetes mellitus should be taken off treatment.
Patients may develop symptomatic and radiologic evidence of pancreatitis as well as diabetes mellitus and diabetic ketoacidosis (DKA). Lipase elevation may occur during the period of steroid withdrawal and with other immune-mediated events or associated with colitis, hepatitis, and patients who have asymptomatic lipase elevation typically have self-limited course and may be retreated.	

For treatment management of symptomatic pancreatitis, please follow the Hepatic AE Management Algorithm.

Pneumonitis	Management/Next Dose for Nivolumab
≤ Grade 1	Hold dose pending evaluation and resolution to baseline including baseline pO 2 . Resume no change in dose after pulmonary and/or infectious disease (ID) consultation excludes lymphocytic pneumonitis.
Grade 2	Hold dose pending evaluation. Resume no change in dose after pulmonary and/or ID consultation excludes ipilimumab and associated lymphocytic pneumonitis as the cause of the pneumonitis. Off study if steroids are required.
Grade 3	Hold dose pending evaluation. Resume no change in dose after pulmonary and/or ID consultation excludes ipilimumab and associated lymphocytic pneumonitis as the cause of the pneumonitis. Off protocol treatment.
Grade 4	Off protocol therapy.
Distinguishing inflammatory pneumonitis is often a diagnosis of exclusion for patients who do not respond to antibiotics and have no causal organism identified, including influenza. Most patients with respiratory failure or hypoxia will be treated with steroids. Bronchoscopy may be required and analysis of lavage fluid for lymphocytic predominance may be helpful. Patients with new lung nodules should be evaluated for sarcoid like granuloma. Please consider recommending seasonal influenza killed vaccine for all patients.	
Recommended management: See Pulmonary AE Management Algorithm	

Other GI Nausea/Vomiting	Management/Next Dose for Nivolumab
≤ Grade 1	No change in dose.
Grade 2	Hold pending evaluation for gastritis, duodenitis, and other immune AEs or other causes. Resume at same dose level after resolution to ≤ Grade 1.
Grade 3	Hold pending evaluation until ≤ Grade 1. Resume at same dose level. If symptoms do not resolve within 7 days with symptomatic treatment, patients should go off protocol therapy.
Grade 4	Off protocol therapy
Patients with Grade 2 or 3 N-V should be evaluated for upper GI inflammation and other immune related events.	

Fatigue	Management/Next Dose for Nivolumab
Grade 2	No change in dose.
Grade 3	Hold until $\leq$ Grade 2. Resume at same dose level.
Grade 4	Off protocol therapy.
Fatigue is the most common AE associated with immune checkpoint therapy. Grade 2 or greater fatigue should be evaluated for associated or underlying organ involvement including pituitary, thyroid, and hepatic, or muscle (CPK) inflammation.	

Neurologic events	Management/Next Dose for Nivolumab
$\leq$ Grade 1	Hold dose pending evaluation and observation. Resume with no change in dose when resolved to baseline.
Grade 2	Hold dose pending evaluation and observation. Hold until $\leq$ Grade 1. Off protocol therapy if treatment with steroids is required. Resume at same dose level for peripheral isolated n. VII (Bell's palsy).
Grade 3	Off protocol therapy.
Grade 4	Off protocol therapy
Patients with any CNS events including aseptic meningitis, encephalitis, symptomatic hypophysitis, or myopathy, peripheral demyelinating neuropathy, cranial neuropathy (other than peripheral n. VII), GB syndrome, and myasthenia gravis should be off study.	
Recommended management: See Neurologic AE Management Algorithm	

Endocrine Hypophysitis Adrenal Insufficiency	Management/Next Dose for Nivolumab
$\leq$ Grade 1	*Hold pending evaluation for evidence of adrenal insufficiency or hypophysitis. Asymptomatic thyroid stimulating hormone (TSH) elevation may continue treatment while evaluating the need for thyroid replacement.
Grade 2	Hold until patients are on a stable replacement hormone regimen. If treated with steroids, patients must be stable off steroids for 2 weeks. Resume at same dose level.
Grade 3	Hold until patients are on a stable replacement hormone regimen. If treated with steroids, patients must be stable off steroids for 2 weeks. Resume at same dose level.
Grade 4	Off protocol therapy.
Note all patients with symptomatic pituitary enlargement, exclusive of hormone deficiency, but including severe headache or enlarged pituitary on MRI should be considered Grade 3 events. Isolated thyroid or testosterone deficiency may be treated as Grade 2 if there are no other associated deficiencies and adrenal function is monitored.	
Please evaluate pituitary function before beginning steroid therapy or replacement therapy of any kind. *Note patients with thyroiditis may be retreated on replacement therapy. Patients	

must be evaluated to rule out pituitary disease prior to initiating thyroid replacement.

Recommended management: See Endocrine Management Algorithm

Renal	Management/Next Dose for Nivolumab
≤ Grade 1	Monitor closely and continue therapy.
Grade 2	Hold until ≤ Grade 1. Resume at same dose level.
Grade 3	Hold until ≤ Grade 1. Resume at same dose level.
Grade 4	Off treatment

Patients with fever should be evaluated as clinically appropriate. Patients may experience isolated fever during infusion reactions or up to several days after infusion. Evaluation over the course of 1-2 weeks should be done for other autoimmune events that may present as fever.

Infusion reaction	Management/Next Dose for Nivolumab
≤ Grade 1	Monitor closely and continue therapy.
Grade 2	Hold until ≤ Grade 1. Resume at same dose level.
Grade 3	Hold until ≤ Grade 1. Resume at same dose level.
Grade 4	Off treatment

Patients with fever should be evaluated as clinically appropriate. Patients may experience isolated fever during infusion reactions or up to several days after infusion. Evaluation over the course of 1-2 weeks should be done for other autoimmune events that may present as fever.

Fever	Management/Next Dose for Nivolumab
≤ Grade 1	Evaluate and continue at same dose level.
Grade 2	Hold until ≤ Grade 1. Resume at same dose level.
Grade 3	Hold until ≤ Grade 1. Resume at same dose level.
Grade 4	Off treatment

Patients with fever should be evaluated as clinically appropriate. Patients may experience isolated fever during infusion reactions or up to several days after infusion. Evaluation over the course of 1-2 weeks should be done for other autoimmune events that may present as fever.

See section 6.7 – Treatment of Nivolumab-Related Infusion Reactions.

Any patients who require additional immune suppressive treatment beyond steroids should go off study treatment.

Prior to starting corticosteroids or hormone replacement for any reason, appropriate

endocrine testing including cortisol, Cortrosyn® adrenocorticotropic hormone (ACTH), thyroid stimulating hormone (TSH), and thyroxine (T4) must be obtained to document baseline.

Please note that in some cases the treatment algorithms recommend steroids if symptoms do not resolve in 7 days. However, this recommendation is not meant to delay steroid treatment at any time it is clinically indicated.

Any patient started on corticosteroids initially, who is determined to not require steroid treatment for an autoimmune AE, may resume therapy after a 2-week observation period without further symptoms at the discretion of the PI or investigator.

Any patient requiring high dose steroids (any dose greater than the equivalent to 20 mg prednisone) will be considered to have experienced a DLT and will be taken off nivolumab. These patients will be allowed to continue receiving decitabine and venetoclax on study.

Patients requiring high dose steroid treatment for autoimmune or inflammatory events should go off study treatment except for a short course of tapering steroids for infusion reaction, skin rash or endocrine events.

Patients with grade 3 thyroiditis and skin rash may continue therapy as for grade 2 events with resolution and stable replacement treatment.

Patients with thyroiditis or hypopituitarism who are stable as above may be restarted with replacement hormones including thyroid hormone and physiologic doses of corticosteroids.

Please note that grading and for hypophysitis with symptoms of headache, visual or neurologic changes or radiologic evidence of pituitary enlargement and other CNS events such as aseptic meningitis or encephalitis should be considered grade 3 events.

Patients may be dose-delayed for evaluation and restarted depending on results.

Any patient started on corticosteroids initially who is determined to not require steroid treatment for an autoimmune adverse event may resume therapy after a 2-week observation period without further symptoms at the discretion of the PI or investigator.

If doses of nivolumab are missed/delayed other than reasons for toxicity, they may be given +2 days of scheduled dose.

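### For a treatment-related grade 3 or 4 cardiac event worked up as suspected myocarditis that returns to baseline, section 7.5 gives opposite instructions on resuming nivolumab

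*Combined protocol and SAP*

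**What the plan says.** Section 7.5 opens its cardiac guidance with bold bullets. One says: "Drug will be permanently discontinued for treatment related grade 3 or 4 cardiac dysfunction". The same bullet adds "grade 2 events that do not recover to baseline or that reoccur" as a further ground for stopping, so recovery is considered for grade 2 only.

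The table that follows is headed "Management/Next Dose for Nivolumab Cardiac Toxicities". It has three rows: below grade 2, grade 2 or higher with suspected myocarditis, and grade 2 or higher with confirmed myocarditis. The suspected row calls for a hold, admission and work-up, and then says: "Initiate high dose methylprednisolone and immune suppression as clinically indicated". It ends: "May resume therapy if there is a return to baseline and myocarditis is excluded or considered unlikely". The confirmed row takes the patient off protocol therapy. A footnote gives the table's scope: "Including CHF, LV systolic dysfunction, Myocarditis, CPK, and troponin".

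Two other rules bear on the same patients:

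- **High-dose steroids (section 6.3 and late in 7.5).** A patient who requires more than the equivalent of 20 mg prednisone "will be considered to have experienced a DLT and will be taken off nivolumab". Section 7.5 also lets a patient who was started on steroids, and then found not to need them for an autoimmune event, resume after two weeks of observation.
- **Restart after a non-hematologic DLT (section 7.1).** "Patients may restart therapy when the adverse event recovers to CTCAE" grade 1 or lower, or to the patient's baseline. Section 7.1 then refers the reader to the nivolumab-specific rules, citing section 7.3.

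**The concern.** The bullet and the table row govern the same decision, the next nivolumab dose after a cardiac toxicity. They stand next to each other in one section. The bullet closes the way back for grades 3 and 4; the row leaves it open on stated conditions. Two investigators who each follow the protocol could act in opposite ways on the same patient, and neither would clearly be deviating.

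What is at stake is re-exposure to nivolumab after a serious cardiac event. The protocol notes that immune-mediated myocarditis has been fatal and advises an aggressive approach. The row allows resumption when myocarditis is only judged unlikely, so the unsettled cases include some in which that diagnosis has not been ruled out.

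**Working it through.** No arithmetic applies: the point depends on no rate, sample size or error level. The check is to put each kind of cardiac event through both rules.

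| Event | Bold bullet | Cardiac table | Result |
|---|---|---|---|
| Grade 3-4, treatment related, myocarditis confirmed | Stop permanently | Off protocol therapy | Agree on nivolumab |
| Grade 2, suspected, back to baseline, no recurrence | No permanent stop | May resume | Agree |
| Grade 3-4, treatment related, myocarditis never suspected | Stop permanently | No row grants resumption | No conflict |
| Grade 3-4, treatment related, suspected, not back to baseline | Stop permanently | Condition for resuming not met | No conflict |
| Grade 3-4, suspected, then attributed to a cause other than treatment | Does not apply | May resume at baseline | No conflict |
| Grade 3-4, treatment related, suspected, back to baseline, myocarditis excluded or judged unlikely | Stop permanently | May resume | **Opposite** |

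Three steps support the last line.

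1. **The row includes grades 3 and 4.** It starts at grade 2 and has no upper limit. Most other toxicity tables in 7.5 give grades 2, 3 and 4 separate rows, so limiting this row to grade 2 would have been easy.
2. **An event can be treatment related without being myocarditis.** The footnote brings in heart failure, left ventricular dysfunction, CPK and troponin, and the header calls all of these nivolumab cardiac toxicities. Excluding myocarditis therefore does not take an event outside the bullet.
3. **Nothing visible ranks the two rules.** The opening of 7.5 allows the treating physician to depart from the Investigator Brochure and Appendix E algorithms. It does not say whether the bullet or the table governs.

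The steroid rule narrows the last line. A patient in that row who requires high-dose steroids is taken off nivolumab whatever the row says. The conflict stays open for patients who did not require high-dose steroids, including those started on them and later found not to need them.

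**The case against.** The strongest reply is that the bullets and table form a sequence. Drug is held for evaluation; a mandatory bullet stops it for treatment-related grade 3 or 4 events; the row is a diagnostic work-up ending in permission, and permission need not override a mandatory rule. On this reading, resumption serves grade 2 events that recover and events the work-up attributes elsewhere. The reading is possible, but the text does not state it. The row is open-ended by grade, sits under a header about nivolumab toxicities, and requires only that myocarditis be judged unlikely.

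Other points on that side stand and set the limits here:

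- A reader might infer that every treatment-related grade 3 or 4 cardiac event short of confirmed myocarditis is affected. The text does not support this: the row grants resumption only if myocarditis was suspected and the patient returned to baseline.
- A reader might count section 7.1 as a second rule that permits rechallenge. It is a general rule that defers to the nivolumab section. Its defect is the pointer: it cites 7.3, which now covers missed doses of decitabine and venetoclax, while nivolumab is in 7.5.
- A reader might infer that DLT counts or the MTD are at risk. Section 6.3 classifies a DLT by the event, not by whether drug is later resumed, so no effect on the 3+3 decisions is shown.
- The note about deaths concerns immune-mediated myocarditis, and for confirmed cases the rules do not conflict.
- Section 7.5 tells sites to follow Appendix E. The myocarditis figure there is not in the supplied text and may contain a graded rule. Even so, the bullet and the row would still disagree within 7.5.

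**Conclusion.** The contradiction is real and confined to one kind of patient: a treatment-related grade 3 or 4 cardiac event, worked up as suspected myocarditis, back at baseline, with myocarditis excluded or judged unlikely, and not already removed under the high-dose-steroid rule. For that patient section 7.5 says both that nivolumab is stopped for good and that it may be resumed.

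The frequency cannot be derived from the documents. As a rough guide only, the nivolumab risk list in section 10.1.1 puts myocarditis and cardiomyopathy in its column for events below 3%. If that ceiling carried over to this regimen, which is an assumption, it would mean fewer than 0.03 × 42 = 1.26 patients per term at the maximum enrolment in section 9.2. The suspected cases that turn out not to be myocarditis are not captured by that figure.

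The case for acting therefore rests on the seriousness of the event and the low cost of the repair, not on numbers. The conclusion assumes that no precedence rule stands in the Appendix E figure. It takes no position on which instruction is clinically right.

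**What to change.** Reconcile the bold bullet and the suspected-myocarditis row into one rule that states, by grade, whether nivolumab may be resumed when myocarditis is not confirmed, and remove whichever sentence no longer applies. The same rule should say how a recurrent grade 2 event is handled, since the bullet mentions recurrence and the row does not.

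Make it consistent with the high-dose-steroid rule in sections 6.3 and 7.5 and with the Appendix E myocarditis algorithm. Correct the cross-reference in 7.1 from 7.3 to 7.5. The clinical choice belongs to the sponsor.

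The cost is a wording amendment to 7.5 and a corrected pointer in 7.1, plus notice to sites. No sample size, endpoint or analysis changes.
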